### **6.4.2 Inclusion criteria**

Participants able to provide informed consent who have consented to being contacted for the biosampling/wearable study and able to undertake the protocol activities.

### **6.4.3 Exclusion criteria**

Participants who have not previously consented to be contacted for bio-sampling/use of wearables.

Participants unable/unwilling to provide informed consent.

Participants unable/unwilling to undertake the protocol activities.

## **6.5 Co-production workshops**

### **6.5.1 Eligibility Criteria**

Patients and their family members, healthcare professionals, experts in relevant symptoms and corresponding interventions, regulators, and policymakers (NICE).

### **6.5.2 Inclusion criteria**

Individuals able to provide informed consent who have an interest in treatments for Long COVID, including people who have experienced Long COVID and their family members, friends or carers; healthcare professionals; experts in symptom management and potential treatments relevant to Long COVID; and academic researchers.

### **6.5.3 Exclusion criteria**

Individuals unable/unwilling to provide informed consent.

Individuals unable/unwilling to attend a co-production workshop.

## **6.5 Participant identification and recruitment**

6.5.1 Population-based representative cohort of individuals with Long COVID

[figure not shown]
Researchers from The University of Birmingham will use linked data from the Second-Generation Surveillance (SGSS) data that contain SARS CoV-2 positive RT-PCR results to identify patients with confirmed COVID-19 in CPRD Aurum. Using linked Hospital Episode Statistics (HES), the research team will identify and exclude patients who have been hospitalised within 28 days of a positive SARS CoV-2 RT-PCR result or COVID-19 diagnosis).

The list of CPRD Aurum IDs of patients identified as potentially eligible (as above) by the research team will be provided to CPRD. The list of suitable patients will then be uploaded onto the CPRD Interventional Research Services Platform (IRSP). IRSP will generate a unique “username” (Global ID) for each patient on that list, which will be shared with Aparito to assist with verifying participants registering on the Atom5™ app. CPRD will inform participating GP practices that the patient list is available for them to review on by logging onto IRSP. GPs will identify the patients using the corresponding EMIS ID and screen them for their suitability for this study. Researchers at the University of Birmingham will not have access to Patient Identifiable Data until they have consented to participate on Atom5™.

GPs will then invite eligible patients to take part via invitation letters, text message or email which will contain the patient information sheet (PIS) and a username and unique one time password for the Aparito Atom5™ platform. Patients will then log on Atom5™ and provide e-consent (which includes confirming their eligibility) and log data on their symptoms and patient-reported outcomes (PROs). From this data we will identify individuals with prolonged symptoms (>12 weeks) associated with COVID-19, which will form the long COVID cohort.

Participants will be provided a £10 Amazon voucher code via Atom5™ upon completing the baseline questionnaires and a further £10 Amazon voucher upon completing the final study questionnaires at 12 months of follow-up.

**Figure 2.0 Participant recruitment**

### **6.5.2 Matched controls**

Sampling from the CPRD Aurum database, we will generate a propensity score matched control population of 500 individuals without a positive SARS CoV-2 RT-PCR result (Control Group 1) and 500 individuals with COVID-19 without Long COVID (Control Group 2), to assess the additional burden of Long COVID symptoms beyond what is observed in the infected population. Propensity scores will be generated using data on sociodemographic factors, lifestyle and metabolic profile measures and comorbidities. Matching will be done using the nearest-neighbour algorithm without replacement, considering callipers of width equal to 0.1. The index date for matching will be 1st January 2020. The CPRD Aurum ID for the matched control patients within Control Group 1 will be provided to the CPRD IRSP. CPRD will inform participating GP practices of these patients by providing the corresponding EMIS codes and will ask them to check their suitability for recruitment. The list of suitable patients will then be recorded on IRSP with the generation of a unique Global ID. Researchers at the University of Birmingham will not have access to Patient Identifiable Data until they have consented to participate on Atom5™. Participating GP's will invite eligible patients to take part via invitation letters, text message or email which will contain a copy of the PIS and a unique on-boarding code. Patients willing to take part will be instructed to use the on-boarding code to register on the Atom5™ platform.

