### 1.0 Background

Coronavirus Disease 2019 (COVID-19), caused by Severe Acute Respiratory Syndrome Coronavirus 2 (SARS CoV-2), is the most significant pandemic since the Spanish Influenza Pandemic of 1918. There have been over 140 million cases worldwide, including over 4.4 million cases in the UK. In the UK, this has resulted in over 460,000 hospital admissions and in excess of 150,000 deaths.

SARS CoV-2 enters human cells using the angiotensin II receptor, which is widely expressed throughout the body. COVID-19 is consequently a multisystem disorder affecting the lungs, heart, gut, kidneys, brain and skin. A wide range of symptoms have been associated with COVID-19 including breathlessness, fatigue, fever, myalgia, “brain fog” and anosmia.

These symptoms resolve within 12 weeks in most affected individuals. However, in up to 10% of individuals, symptoms of COVID-19 persist, sometimes in a relapsing remitting manner. This can have significant impacts on physical and neurocognitive functioning, quality of life and work capability. Those having symptoms lasting beyond 12 weeks are referred to as experiencing post-COVID-19 syndrome (NICE 2019) or more widely known as Long COVID.

The cause of Long COVID is poorly understood. However, there is evidence from other post-viral syndromes that may be applicable to Long COVID. Furthermore, evidence from existing studies on COVID-19 suggest a significant burden of pathophysiological insults and sequelae such as lung scarring, kidney injury, myocarditis and systemic inflammatory states that may promulgate longer term symptoms. There is also a possibility that autoimmune pathways may be triggered by COVID-19, leading to multi-system inflammatory damage.

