### **Second-Generation Surveillance System (SGSS)**

SGSS is the national laboratory reporting system used in England to capture routine laboratory data on infectious diseases and antimicrobial resistance. The SARS-CoV-2 testing started in UK laboratories on 24/02/2020, with the SGSS data reflecting testing (swab samples, PCR test method) offered to those in hospital and NHS key workers (i.e., Pillar 1). The linked SGSS data only contains positive tests results. The primary care data itself includes both positive and negative Pillar 2 PCR and other RNA detection COVID-19 test results and it is estimated that over 80% of all such tests undertaken in England are being matched to GP records.

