## **6.3 Matched controls - Group 2 (50 participants)**

### **6.3.1 Eligibility criteria**

Participants taking part in the study who have had a positive SARS CoV-2 RT-PCR test result in SGSS data linked to CPRD but not reporting symptoms on ATOM5™ beyond 12 weeks from the positive RT-PCR test result will comprise Control Group 1. These control participants will be propensity score-matched to participating Long COVID patients.

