## **6.4 Bio-sampling and wearables (BioWear) cohort (200 Long COVID participants, 50 participants from Control Group 1 and 50 participants from Control Group 2)**

### **6.4.1 Eligibility Criteria**

Participants in the study who have self-reported symptoms associated with COVID-19 more than 12 weeks since a positive SARS CoV-2 RT-PCR test or COVID-19 diagnosis. This will include 50 randomly sampled participants from each Long COVID symptom cluster, up to a maximum of 200 Long COVID participants. 50 participants randomly sampled from Control Group 1 and 50 participants randomly sampled from Control Group 2 will also be eligible.

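### Control Group 2 is matched to Long COVID participants without the date of the positive test, leaving the biomarker contrasts open to confounding by time since infection

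*Protocol*

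**What the plan says.** Section 6.3.1 defines Control Group 2 as study participants with a positive PCR test "but not reporting symptoms on ATOM5™ beyond 12 weeks from the positive RT-PCR test result", and adds: "These control participants will be propensity score-matched to participating Long COVID patients".

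Section 6.5.2 sets out the match for both control groups. On covariates: "Propensity scores will be generated using data on sociodemographic factors, lifestyle and metabolic profile measures and comorbidities". On method: "Matching will be done using the nearest-neighbour algorithm without replacement, considering callipers of width equal to 0.1". It then fixes one index date for everyone ("The index date for matching will be" 1 January 2020).

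On the possible spread of infection dates, Box 1 says of the surveillance data: "The SARS-CoV-2 testing started in UK laboratories on 24/02/2020". The version log dates the protocol 05/07/2021. Sections 6.1.1, 6.3.1 and 6.4.1 use a 12-week threshold and give no maximum time since the positive test.

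For the BioWear sub-study, section 6.4.1 says: "50 participants randomly sampled from Control Group 1 and 50 participants randomly sampled from Control Group 2 will also be eligible". Section 11.1 times the bio-sampling invitation at three months after enrolment, not from infection.

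**The concern.** Long COVID participants and Control Group 2 come from the same PCR-positive cohort. They are separated by what they report on Atom5 after registering. The symptom questionnaire (SBQ-LC, section 9.1) asks about the last 7 days, so a person whose prolonged symptoms cleared before a late registration can be counted in Control Group 2. Group membership can therefore depend on how long ago the infection was, and the match does not balance that. Covariates measured at 1 January 2020 cannot stand in for it.

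Control Group 2 is the infected comparator for the autoantibody, T-cell, protein and small-RNA work. Section 11.4 intends to use those results to point to candidate drugs. If a marker varies with time since infection, or with what goes with calendar period (such as vaccination), a difference that only reflects when people were infected could be read as a feature of Long COVID.

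**Working it through.** **1. Time span.** From 24/02/2020 to 05/07/2021 is 366 + 131 = 497 days, which is 71 weeks or about 16.3 months. At the protocol date a Long COVID participant could be 12 to 71 weeks from the test, and later enrolment widens this. The index date of 1 January 2020 is 54 days before the first testing date.

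**2. The plan's own power table.** Table 3 (section 14.2; Kruskal-Wallis, 50 v 50, alpha 0.05) was re-simulated with 20,000 replicates. Normal data gave 16.0%, 30.7% and 49.1% at d = 0.2, 0.3 and 0.4, against 16.3%, 30.5% and 48.4% stated. The largest gap is at d = 0.6 (82.8% v 80.8%). The t5 column agrees within 1 point. Table 3 can therefore be used to read off how often a spurious shift would be declared significant.

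**3. Possible imbalance (assumed, not in the documents).** Let time since infection t be uniform on 3 to 16 months at registration (mean 9.5, variance 13²/12 = 14.08). Let p(t) be the probability of still reporting symptoms, 20% at 3 months. Weight t by p for Long COVID and by 1 − p for Control Group 2. The standardised difference is the gap in means over the root of the average variance.

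Worked case: p falls linearly to 5% at 16 months, so the slope is −0.15/13 = −0.01154 and mean p is 0.125.
- Long COVID mean = 9.5 − 0.01154 × 14.08/0.125 = 8.20 months.
- Control Group 2 mean = 9.5 + 0.01154 × 14.08/0.875 = 9.69 months.
- SDs are 3.52 and 3.75, so the difference is 1.49/3.64 = 0.41.

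Other curves over the same span: halving every 4 months gives means of 7.24 and 9.70 and a difference of 0.69; halving every 8 months gives 0.37; halving every 24 months gives 0.13; a flat curve gives 0. With infections confined to 3 to 12 months, the same linear, 4-month and 8-month curves give 0.24, 0.50 and 0.26.

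**4. Spurious shift and false-positive rate.** With no true group effect, d = imbalance × correlation of the marker with time. For n = 50 per group the rejection rate is approximately Φ(d√(n/2)√0.955 − 1.96) + Φ(−d√(n/2)√0.955 − 1.96), where 0.955 is the efficiency of the rank test under normality.

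| Imbalance (SD) | r = 0.1 | r = 0.3 | r = 0.5 |
|---|---|---|---|
| 0.13 | d 0.01, 5.0% | d 0.04, 5.4% | d 0.07, 6.2% |
| 0.37 | d 0.04, 5.4% | d 0.11, 8.4% | d 0.18, 14.7% |
| 0.41 | d 0.04, 5.5% | d 0.12, 9.2% | d 0.20, 17.0% |
| 0.69 | d 0.07, 6.3% | d 0.21, 17.4% | d 0.35, 39.5% |

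Table 3 brackets the extreme corner: 30.5% at d = 0.3 and 48.4% at d = 0.4. If time since infection is balanced or adjusted for, d from this source is 0 and the rate returns to 5%.

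**The case against.** Several objections stand and limit the point.

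- **Confounding is not shown.** A reader might infer that the contrasts are confounded, with Long COVID participants the more recently infected. The documents give no infection dates by group, and both groups come from one recruited cohort.
- **The Background does not give the direction.** It says: "These symptoms resolve within 12 weeks in most affected individuals". That is resolution before the Long COVID threshold. For those beyond it, the same section describes persistence, sometimes relapsing and remitting. If persistence is flat after 12 weeks, the imbalance is 0.
- **A uniform 3 to 16 months is probably generous.** Box 1 says the surveillance data reflect tests offered to people in hospital and NHS key workers, and patients admitted within 28 days are excluded. Early eligible infections may be few.
- **The symptom contrast is a weak target.** Control Group 2 is defined by not reporting symptoms, so most of that difference is built in. Matching on test date would not alter it.
- **Some of this could be handled elsewhere.** Vaccination status is collected at baseline and monthly (Table 1.0), comparisons between syndromes do not use Control Group 2, and an analysis plan could adjust for test date.

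The last objection does not remove the point. The protocol itself fixes the covariate classes, the index date and the random BioWear draw. If 50 controls overlap poorly with cases on infection date, adjustment afterwards is weak.

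**Conclusion.** The point holds for the biomarker contrasts between Long COVID and Control Group 2. The stated match omits a variable on which group membership may depend, and nothing else in the protocol balances it. It does not concern Control Group 1, which has no infection to date.

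The effect could be negligible or material. Across the assumed imbalance of 0.1 to 0.7 SD and marker correlation of 0.1 to 0.5, the spurious shift is about d = 0.01 to 0.35. The false-positive rate at 50 v 50 runs from about 5% to about 40%. The upper end needs both the fastest assumed decline and the highest assumed correlation; most combinations in the table stay below 18%. These inputs are assumptions, and the documents settle neither the size nor the direction. This is a cheap improvement that should be made before the match is run. It is not evidence that the comparison will fail.

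**What to change.** In sections 6.3.1 and 6.5.2, add time from the positive SARS-CoV-2 test to registration, or calendar period of infection, to the propensity model for Control Group 2. Alternatively, match on it within a stated window. State that the Long COVID versus Control Group 2 biomarker comparisons will be adjusted for it.

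Frequency-matching the 50 Control Group 2 BioWear participants on time since test (sections 6.4.1 and 6.5.3) is optional. A random draw is adequate if the group is already balanced or the analysis is adjusted.

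The cost is protocol wording and slightly fewer acceptable matches within the calliper. Cases are identified from the linked SGSS and CPRD data by their positive test, so the date should already be held.

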Patients with COVID-19 will be propensity score matched to patients without a COVID-19 diagnosis (minimum n=500), who will similarly be invited to participate in the study following eligibility checking by their general practice. This will constitute control group 1. Propensity scores will be estimated for the likelihood of COVID-19 using logistic regression, including the following data obtained from CPRD Aurum: age, sex, socio-economic status, body mass index (BMI), smoking status, comorbidities and risk factors for COVID-19 identified by Public Health England. A second control group of at least 500 participants will be derived from those with COVID-19 who do not report long-term symptoms (i.e., do not have Long COVID).

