**Data-driven analysis to identify distinct Long COVID syndromes (Objective 4, part A)**

We will define distinct symptom clusters (syndromes) using linked data from CPRD and Atom5™ platforms. We will employ clustering algorithms that have been shown to work well in medical settings, with binary and mixed variables: (1) complete linkage hierarchical clustering; (2) probabilistic c-means cluster analysis; (3) density peaked clustering analysis. We will evaluate algorithm performance and the optimal number of clusters (e.g. by internal validation against a holdout dataset using metrics such as Gap statistic and silhouette index).

We will describe the epidemiology of patients within each Long COVID syndrome as well as health service use (primary care consultations, prescriptions, A&E attendances and hospital admissions) and mortality risk and compare these to both sets of matched control patients. We will identify whether Long COVID syndromes are

associated with particular population groups such as BAME groups, patients with long-term conditions, and other vulnerable population groups identified by Public Health England.

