#### 6.1.3 Exclusion criteria

Individuals without a positive SARS CoV-2 RT-PCR test result in CPRD Aurum.

Individuals with a hospital admission within 28 days of a positive SARS CoV-2 RT-PCR result in CPRD AURUM.

Individuals aged under 18 years.

Individuals unable/unwilling to provide informed consent.

Individuals unable/unwilling to undertake the protocol activities.

Individuals deemed appropriate for exclusion by their GP (e.g., on a palliative care register).

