## **6.2 Matched controls - Group 1 (minimum of 500 participants)**

### **6.2.1 Eligibility Criteria**

Propensity score-matched individuals without a diagnosis of COVID-19 (suspected or confirmed) in CPRD Aurum and without a positive SARS CoV-2 RT-PCR result in linked SGSS data and without a record of hospital admission within 28 days of the index date will comprise Control Group 1. For propensity score matching we will use covariates such as sociodemographic characteristics, lifestyle and metabolic profile measures and presence of comorbidities, especially those identified as risk factors for COVID-19.

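### Control Group 1 is matched to all COVID-19 patients but compared with Long COVID participants, and its admission screen rests on a pre-pandemic index date

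*Protocol*

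**What the plan says.** **Matching of Control Group 1.** Section 5.0 (WP1, Objective 1) matches patients with COVID-19 to patients without that diagnosis: "Propensity scores will be estimated for the likelihood of COVID-19 using logistic regression". Section 6.5.2 places this step in CPRD Aurum, before general practices check and invite the controls. Section 6.5.1 forms the Long COVID cohort afterwards, from data that consented participants enter on Atom5.

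**Matching of Control Group 2.** Section 6.3.1 matches these controls to participating Long COVID patients. Its text calls them Control Group 1, but the section heading and the requirement for a positive test show that Group 2 is meant.

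**Planned contrasts.** WP2 (Objective 4, part A) will describe health service use and mortality risk for each Long COVID syndrome and "compare these to both sets of matched control patients". Section 10.2 compares SBQ-LC scores between Long COVID and matched controls (known-groups validity), and uses the same two sides for the ROC curve and cut-off values.

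**Admission screens.** Section 6.1.3 excludes from the COVID-19 cohort "Individuals with a hospital admission within 28 days of a positive SARS CoV-2 RT-PCR result in CPRD AURUM". For Group 1, section 6.2.1 requires people "without a record of hospital admission within 28 days of the index date". The only index date defined in the protocol is in section 6.5.2: "The index date for matching will be" 1 January 2020. Box 1 states: "The SARS-CoV-2 testing started in UK laboratories on 24/02/2020".

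**The concern.** A propensity match balances the two populations that enter the model. Here those are people with and without COVID-19. Long COVID participants are a later, selected subset of the first population. Section 2.0 cites higher prevalence in women, older adults and people with specific symptom clusters. A Group 1 that mirrors all COVID-19 patients can then differ from the Long COVID group in age and sex while being reported as matched. Consent after matching can disturb the balance further on both sides.

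The quantities exposed are those where Group 1 serves as the uninfected reference: health service use, mortality risk, and the SBQ-LC comparisons and cut-offs if Group 1 is among the matched controls used there.

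The admission screen is a second, separate matter. If both groups are to count as non-hospitalised, the rule should look at comparable periods. As written, cases are screened around their own infection and controls around New Year 2020.

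**Working it through.** The plan states no figure to reproduce on this point. The check is date arithmetic plus a comparison of matching target with contrast.

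**A. Admission windows**

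Inputs: index date 1 January 2020 (6.5.2); 28 days (6.2.1 and 6.1.3); testing from 24 February 2020 (Box 1).

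1. Control window, read in both directions: 1 January 2020 − 28 days = 4 December 2019; 1 January 2020 + 28 days = 29 January 2020.
2. Gap to the first possible positive test: 29 January to 24 February 2020 = 26 days.
3. If the case window runs forward from the test, it opens on 24 February 2020 at the earliest, so there is no overlap.
4. If the case window runs both ways, the earliest one opens on 24 February − 28 days = 27 January 2020. The overlap is 27 to 29 January, three calendar days, and only for cases testing positive on 24 to 26 February 2020.

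Sections 6.2.2 and 6.2.3 do not repeat the admission rule for controls, and Table 1.0 asks the admission question of cases only. Section 6.2.1 therefore carries the control rule alone.

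**B. Matching target against contrast**

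| | Matched to | When | Compared with |
|---|---|---|---|
| Group 1 | all COVID-19 patients | in CPRD, before invitation | Long COVID syndromes (WP2) |
| Group 2 | participating Long COVID patients | once Atom5 symptom reports exist | Long COVID syndromes (WP2) |

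Share p of the COVID-19 cohort that has Long COVID, on the protocol's sizes (Long COVID minimum 500, aim 750; COVID-19 minimum 2000, aim 4000):

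- 500/4000 = 12.5%
- 750/4000 = 18.75%
- 500/2000 = 25%
- 750/2000 = 37.5%

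If 500 controls are matched 1:1 (the ratio is an assumption), the number whose COVID-19 partner has Long COVID is 500 × p, from 62.5 to 187.5, and 125 at the stated minimums. Most controls would mirror someone without Long COVID.

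**C. What the match can leave behind (illustration)**

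Let d be the standardised difference on a covariate between Long COVID and other COVID-19 patients. If Group 1 reproduces the mean of all COVID-19 patients exactly, the remaining difference between Long COVID and Group 1 is d × (1 − p). The protocol gives no value for d, so a range is shown:

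| assumed d | p = 12.5% | p = 25% | p = 37.5% |
|---|---|---|---|
| 0.1 | 0.09 | 0.08 | 0.06 |
| 0.2 | 0.18 | 0.15 | 0.13 |
| 0.3 | 0.26 | 0.23 | 0.19 |
| 0.5 | 0.44 | 0.38 | 0.31 |

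This also assumes a common standard deviation and the same p in the matching target as in the enrolled cohort. With p at the 10% quoted in section 1.0, d = 0.3 leaves 0.27. For d of 0.2 or more, every entry exceeds the commonly used balance limit of 0.10. For d = 0.1, none does.

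**The case against.** Several counter-arguments carry weight.

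- **The date may be only the covariate date.** Section 6.5.2 speaks of an index date for matching. A pre-pandemic date is sound for that, since it avoids adjusting for values that infection has altered. This stands, and 1 January 2020 is not in itself a mistake. But section 6.2.1 relies on an index date that is defined nowhere else, so the text needs correcting on either reading.
- **A reader might infer that the two admission windows cannot overlap at all.** That holds only if case windows run forward, and the protocol gives no direction. Up to three days of overlap are possible.
- **No bias from the screen is shown.** Never-infected controls have no COVID-19 admission to remove, and the questionnaires are collected long after January 2020. The 26 days describe a mismatch of rules, not an effect on an estimate.
- **A reader might infer that no contrast is matched to Long COVID.** Group 2 is. The criticism reaches Group 1 only.
- **Group 1 could not have been matched to Long COVID at recruitment,** because that status is unknown then. This is correct, and it is why the remedy comes after enrolment.
- **Adjustment may sit in a statistical analysis plan that is not shown.** That is possible, and the protocol does not say that the comparisons will be unadjusted. However, the matching target and index date are fixed here, and the known-groups and ROC paragraphs in section 10.2 describe parametric tests and curves without covariates. They also say only matched controls, without naming the group, so Group 1's role there is likely but not explicit.

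**Conclusion.** The point holds in two limited parts.

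First, the Group 1 match does not secure balance for Long COVID versus Group 1. This follows from the order of steps and from the modelled outcome, and needs no assumed figure. The protocol's own rationale gives reason to expect differences in sex and age. It does not name comorbidity, so an imbalance there should not be presumed. A reader might conclude that these comparisons will be confounded by a known amount. The documents do not support that: the table in the working rests on assumed values of d, and an unseen analysis plan may adjust.

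Second, as written, the admission screen for Group 1 covers 4 December 2019 to 29 January 2020. It ends 26 days before testing began and shares at most three days with any case window. Its effect on results is not quantified and may be small.

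Both parts merit correction because the remedy is cheap and uses covariates already planned for extraction.

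**What to change.** 1. **Separate the two dates.** In section 6.5.2, name 1 January 2020 as the date at which matching covariates are measured. In section 6.2.1, give each Group 1 control the positive-test date of its matched case as the index date for the 28-day admission screen. State in sections 6.1.3 and 6.2.1 whether the window runs forward only or both ways.
2. **Rebalance for the contrast actually made.** For Long COVID versus Group 1, re-match or weight enrolled Group 1 participants to enrolled Long COVID participants on the same CPRD covariates. Report standardised differences before and after, and adjust the comparison for those covariates. State in section 10.2 which control group each SBQ-LC comparison uses.
3. **Keep the existing match for its own contrast:** all PCR-positive participants versus Group 1.

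The cost is a short edit to the eligibility text, a little more analysis, and some loss of effective sample size from re-matching or weighting. The effective size should be reported beside the nominal one.
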